#### 14.2 Quality Control of Data

Through-out the study conduct study data will be subject to review by members of the study team that have no direct relation to the obtained data. Data cleaning measures will be considered at the point of data entry. Transcript of data from the CRF or source document to the study database will be checked. Discrepancies found will be collected on data correction forms and appropriate actions taken for them will be documented and those who are found nonredeemable will be justified as appropriate.

#### **14.3 Deviations and Violations**

No intentional deviations or violations of the study will be made by the investigator or the study team without going to the appropriate channels for approval (i.e. IRB). Those deviations and violations that occur beyond the control of the investigator or the study team will be documented and reported. Any corrective or preventive actions made will also be described. If the violation or the deviation concerns the study patients the investigator will inform the IRB in writing about the incident as detailed as possible. The investigator judgment will be exercised to whether or not the deviations or violations have adverse effect on the safety of patients or the outcome of the study and hence if there is a need to terminate the patient participation or the study as a whole.

#### **14.4 Retention of Documents**

After the study ends, all study documents will be retained at the clinical trial unit office archives for a minimum period of five years post issue of publication. The investigator will then consider if the period of retention needs to be extended any further beyond the retention end date. If the study documents are to be destroyed the destruction will be documented for future reference.

PRT-INM-0615/09 V06

# 15. Reporting and Publication

#### **15.1 Progress and Final Reports**

Progress reports about the study conduct will be prepared at the clinical trials unit. The reports will include breakdown of screening, enrolment and withdrawal status of subjects, as well as, a summary of safety issues and deviations. These reports will be sent to the IRB in each quarter.

A final report of the study conduct and study results will be prepared at the end of the study at the clinical trials unit. The report will be submitted to the IRB after publication of results.

#### **15.2 Publication of Results**

KHCC is the sole proprietor of the study data. The Principal Investigator has the right to publish the outcome of the study in any medical journal he sees befitting. The investigator will follow the rules and regulations on authorship defined by KHCC. The principal investigator will be the first and corresponding author. The investigator will follow the CONSORT statement format for reporting clinical trials. Once the publication is made the investigator will provide notice to the IRB about it.

## 16. Ethical Considerations

#### 16.1 Risk to Benefit Analysis

FCM has been reported to be well tolerated with no significant adverse side effects The most common (≥1/100 to <1/10) adverse effects reported from trials and marketing experience are headache, nausea, hypertension, injection site reactions (pain, bruising, discolorations), mild increase in alanine aminotransferase and Hypophosphataemia. A single dose between 500 mg and 1000 mg is only expected to last 72 hours (terminal half-life between 7 to 12 hours). Adverse reactions, if happened, are transient and can be managed.

On the other hand, if a short course of FCM (one or two treatments) proves to be effective and hepcidin and/or CRP are proved as effective predictors of response; we will then have an effective treatment for anemia and we will be able to find methods to make the distinction between patients who are likely to respond and those who are not.

#### **16.2 Institutional Review Board**

The IRB of KHCC will review the study protocol and provide their favorable opinion on the study conduct. The study will not start without gaining the IRB approval first. The PI is responsible to assure that all documents necessary for the IRB review and issue of judgment will be supplied without delay. The investigator will not do changes to an already approved protocol without discussing it first with the IRB through a written amendment request unless it was necessary to remove an immediate hazard to the study patients or the change was of a logistical ground such as the change of phone numbers.

The investigator will also be responsible to report all AE to the IRB according to KHCC policies and procedures. The final outcome of the study will be provided in a written summary report within a reasonable time span.

#### 16.3 Ethical Conduct of the Study

The study will be conducted in accordance with ethical principles that have their origins enunciated in the Declaration of Helsinki, adopted by the General Assembly of the World Medical Association (WMA), Helsinki, Finland (1964) and amended by the 59th WMA General Assembly, Seoul, 2008. The study will be conducted in accordance with the protocol and the ICH guideline on Good Clinical Practice topic E6.

#### **16.4 Informed Consent**

Patients will not be allowed to participate in the study and carry out any of the study procedures before they have been properly informed of all aspects of the study, roles and expectation, risks and benefits through a thorough consent procedure. The study patients will be required to sign a consent form establishing their agreement to participate in the study and that they have understood all implications and attributes of the study. If for reasons of illiteracy the patient is unable to sign the consent him/herself, a legally accepted representative will be required to attend the consent procedure and sign on behalf of the patient's guardian. The signed consent document will be retained in the study file and another signed copy of the consent will be given back to the patient.

Patients will not be coerced to participate in the study by the investigator or the study team. The patients will be given the freedom to review and consider the study before they provide their decision. The decisions to participate or not will neither affect the patients in terms of care and treatment nor will it deprive them from benefits to which they are entitled. Patients will be free to withdraw at any time without any prejudices held against them in any way or to their right to appropriate counseling and management of their case.

The consent form will be prepared in the Arabic language that is considered the native language in Jordan. The level of the text will be prepared at that of an 8th grader. The consent will fulfill the elements of informed consent specified in the US FDA code of federal regulation (CFR) on the protection of human subjects 21 CFR Part 46.116.

#### **16.5 Confidentiality and Privacy**

Patients will be introduced to the study during the hospitalization or their out-patient clinic visits. The study discussion and consent will be held in a private area such as an office or in the patient bedroom.

Throughout the study the patients' identity and data collected for the study will be kept confidential among the study team delegated by the investigator to conduct the study. The patient will be addressed with an appropriate code and with their initials in all study documentation as appropriate. Access to the patient identity and data will be restricted to the study team and the IRB.

#### 16.6 Rights and Liabilities

For all study related events regardless of causality, patients have the right for appropriate treatment and medication to resolve the event free of charge. Events that are unrelated or are disease related will not be covered or considered for coverage. No one from the study team, investigator or the KHCC will be responsible for self-inflicted injuries, injuries resulting from violating protocol or the study team instructions

that are in the best interest of the patient. Patients coverage for adverse events will be through an arranged insurance contract.

#### **16.7 Premature Termination of the Study**

The study will be terminated if one of the following is met:

- 1) The investigator has decided to stop the study due to high incidence of AE to assure the safety of the patients.
- 2) If the recruitment rate was inefficient or sufficient for the study endpoints to be met.
- 3) The IRB has issued a decision to abort the study for any reason.

The decision to end the patient participation or end the whole study prematurely will be in writing regardless of who made that decision and will be conveyed to the other parties. The patients will have the appropriate follow-up measures done for them before their files are closed.

Official title:

The use of intravenous ferric carboxymaltose (FCM) without erythropoiesis-stimulating agents (ESA) in the treatment of anemia in cancer patients undergoing chemotherapy with or without radiotherapy

NCT number:

NCT04246021

Document date:

September 26, 2019

Statistical Considerations

Sample Size Calculation

Patients will be recruited over a whole year tentatively between February and December, 2016. It is estimated that 2-5 % of encountered patients are anemic and eligible for enrollment.

Assuming at 90 % power, 5 % level of significance, based on previous pilot study: a proportion of responders of 0.54 and a standard deviation of 1.21, a response rate of 50 % or more being clinically meaningful, and testing for superiority; a minim of 25 subjects are required. To account for a 10 % chance for drop-outs the required sample is adjusted to 47.5 and approximated to the nearest tens. A total of fifty subjects will be required for the assessment. Since, each strata will be analyzed separately, and assuming both follow the same assumptions 50 subjects per strata will be recruited to make a total study sample of one hundred.^{1,11}

Recruitment of 100 patients in 10 months is doable.

East 6.3 software was used in the estimation of sample size.

Statistical Analysis for data presentation

Descriptive statistics will be used to present the two groups baseline characteristics and disease information. in addition to the patient's responses after the whole follow up period.

- Analysis will be done for the two groups separately:
 - o **Group I**: Patient with iron-deficiency anemia based on iron studies at base line
 - o **Group II**: Patient with non-iron deficiency anemia
- Hb test results will be presented as mean, median and range through all twelve weeks.
- Average percent change from baseline will be used to show the changes of Hb levels.
 Comparison between means of Hb level will be made between the baseline Hb and Hb levels in the following weeks using Paired T-test.
- Response to IV iron therapy will be assessed in relation to Hepcidin and CRP levels.
- Univariate analysis will be used to assess the effect of patient characteristics and disease information on the response using Chi square test or fisher's exact test.
- Adjusting for all significant factors that may affect the response will be done using Logistic regression.
- Odds ratio out of the Logistic regression will be reported with their corresponding 95% Cl.
- A significance criterion of p < 0.05 will be used in the analysis.

All analyses will be performed using SAS version 9.4 (SAS Institute Inc, Cary, NC).

Safety Analysis

Rate and incidence of adverse events will be analyzed and reported. Number of patients requiring ESA or transfusions will be reported using percentages and counts.

¹ Shein-Chung Chow, Jun Shao and Hansheng Wand, Sample Size Calculations in clinical research

ⁱⁱ Abhays Indrayan, Medical Biostatistics, CRC Press Taylor and Francis 2013.

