#### **6.3 Study Endpoints**

#### **6.3.1 Primary Endpoint:**

- Response Rate: Percentage of patients with Hb increment of at least 1.0 gm/dL.
- Proportion of patients achieving correction of anemia (Hb >11.0 gm/dL)
- The mean Hb change from baseline to week 12

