#### 8.3 Subject Withdrawal

Patients are free to withdraw from the study at any time without prejudice or loss of benefits to which they are otherwise entitled. The investigator may remove a patient from the study if, at his discretion, the participation is seen to jeopardize the patient safety or for administrative or behavioral reasons. Neither the investigator nor the study supporting staff will try to coerce patients to continue participating in the study against their will. The withdrawal case with reasons will be documented. Withdrawn subjects will be replaced to have a complete set of 50 analyzable subjects in each strata.

Additionally, patient will be dropped out and will be considered treatment failure if

- 1 .Receive ESA or blood transfusion for medical reasons not related to the study
- 2. if they Develop a grade IV toxicity of any kind in the week between the initial and the remaining dose that is possibly related to study drug.

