### 13. Statistical Considerations

#### **13.1 Sample Size Calculation**

Patients will be recruited over a whole year tentatively between February and December, 2016. It is estimated that 2-5 % of encountered patients are anemic and eligible for enrollment.

Assuming at 90 % power, 5 % level of significance, based on previous pilot study: a proportion of responders of 0.54 and a standard deviation of 1.21, a response rate of 50 % or more being clinically meaningful, and testing for superiority; a minim of 25 subjects are required. To account for a 10 % chance for drop-outs the required sample is adjusted to 47.5 and approximated to the nearest tens. A total of fifty subjects will be required for the assessment. Since, each strata will be analyzed separately, and assuming both follow the same assumptions 50 subjects per strata will be recruited to make a total study sample of one hundred..

Recruitment of 100 patients in 10 months is doable.

East 6.3 software was used in the estimation of sample size.

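### The stated inputs do not give 25 or 50 patients at 90% power against a 50% response rate, and the two primary proportions have no planned test or confidence interval

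*SAP*

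**What the plan says.** Protocol 6.3.1 lists three primary endpoints without ranking them: "Response Rate: Percentage of patients with Hb increment of at least 1.0 gm/dL"; "Proportion of patients achieving correction of anemia (Hb >11.0 gm/dL"; and "The mean Hb change from baseline to week 12".

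Protocol 13.1, repeated in the SAP, assumes 90% power, a 5% level (sidedness not given) and, from the pilot, "a proportion of responders of 0.54 and a standard deviation of 1.21". It adds "a response rate of 50 % or more being clinically meaningful, and testing for superiority". It reaches a minimum of 25, moves to 47.5 for 10% dropout, rounds to 50, and applies 50 to each of the two iron-status strata, which are analysed separately.

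The analysis text is in the statistical plan of the Protocol Summary, in Protocol 13.2 and in the SAP. For Hb over time it says: "Comparison between means of Hb level will be made between the baseline Hb and Hb levels in the following weeks using Paired T-test". In 13.2 and the SAP, patients' "responses after the whole follow up period" are to be described. Response is then related to hepcidin and CRP by an unspecified method, and to patient and disease factors by chi-square or Fisher tests and logistic regression. The only planned confidence intervals are for the odds ratios.

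Protocol 8.3 states: "Withdrawn subjects will be replaced to have a complete set of 50 analyzable subjects in each strata". A separate paragraph there classes as treatment failures the patients who receive ESA or transfusion, and those with a possibly drug-related grade IV toxicity between the two doses.

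**The concern.** A reader of 13.1 would conclude that 50 patients per stratum give a 90% chance of showing that more than half respond, if the true rate is 54%. If the inputs do not support that, an inconclusive result will look like a failed treatment when the design could never have settled the question.

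The analysis text then leaves the benchmark without an analysis. The one test attached to a primary quantity asks whether mean Hb moved from zero. A stratum could be reported as positive on that test while fewer than half of its patients responded, and nothing in the plan says which result carries the conclusion.

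**Working it through.** **1. Trying to reproduce 25.** Inputs from 13.1: p1 = 0.54, p0 = 0.50, power 90% (z = 1.2816), 5% level (z = 1.645 one-sided or 1.960 two-sided). For one proportion,

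n = [(z_a × √(p0(1 − p0)) + z_b × √(p1(1 − p1))) / (p1 − p0)]²

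- One-sided: [(1.645 × 0.5 + 1.2816 × √(0.54 × 0.46)) / 0.04]² = 1,334.3, so 1,335.
- Two-sided, with 1.960: 1,637.6, so 1,638.

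Using the variance at 0.54 throughout, or the arcsine form, gives 1,330 to 1,336 and 1,632 to 1,639. No form gives 25 or 50.

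**2. The dropout step.** 25 × 1.1 = 27.5 and 25 / 0.9 = 27.8, so about 28. The stated 47.5 is 25 × 1.9.

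**3. What may have been sized.** An SD has no role in a one-sample proportion calculation. If 0.54 is treated as a mean change with SD 1.21, one-sided, n = [(1.645 + 1.2816) × 1.21 / 0.54]² = 43.0. Then 43 × 1.1 = 47.3 and 43 / 0.9 = 47.8, on either side of 47.5. This does not explain the 25: with SD 1.21, 25 patients correspond to a mean change of 0.71 (one-sided) or 0.78 (two-sided).

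**4. What 50 per stratum can show about the rate.** Exact binomial against 50%:

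| | One-sided 5% | Two-sided 5% |
|---|---|---|
| Smallest significant count | 32/50 (tail 0.032; 31/50 gives 0.059) | 33/50 (tail 0.016) |
| Power at a true 54% | 10.0% | 5.8% |
| True rate needed for 90% power | about 71% | about 73% |

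An observed 27/50, which is the assumed 54%, has an exact 95% CI of 39.3% to 68.2%.

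**5. What each primary endpoint gets in the analysis text.**

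| Primary endpoint | Test of the quantity itself | CI |
|---|---|---|
| Hb rise of at least 1.0 g/dL | none | none |
| Hb above 11.0 g/dL | none | none |
| Mean Hb change to week 12 | paired t-test against baseline | none |

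The chi-square, Fisher and logistic analyses use response as an outcome, but they test predictors of response, not its level.

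**6. Paired t-test against the benchmark.** Assumptions not in the documents: 1.21 is the SD of Hb change, changes are normal, response is judged at week 12, n = 50, two-sided 5%.

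- Smallest significant mean rise: t(0.975, 49) × 1.21 / √50 = 0.34 g/dL.
- Response rate = 1 − Φ((1 − mean) / 1.21), which is under 50% for any mean rise below 1.0 g/dL.
- So an observed mean rise from 0.34 up to 1.0 g/dL is significant with an implied response rate under 50%.
- Inside that range, a true mean rise of 0.54 implies 35% responders with t-test power of 87%; 0.70 implies 40% with 98%.
- At the edge of significance the implied rate is 29% (SD 1.0: 0.28 g/dL and 24%; SD 2.0: 0.57 g/dL and 41%).
- For contrast, 54% responders implies a mean rise of 1 + 1.21 × z(0.54) = 1.12 g/dL.

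**7. Denominator, conditional only.** If treatment failures were replaced, and the pilot's 20% transfused share applied, 50 analyzable patients would mean 50 / 0.8 = 62.5 enrolled. Then 27 responders would be 27 / 62.5 = 43% of those enrolled, against 54% of those analyzable.

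**The case against.** The best defence is that 13.1 never writes a null hypothesis of 50%. That figure can be read as a benchmark for the observed rate, which 27/50 would meet. If the trial was really sized on mean change, the paired t-test is the matching analysis and the fault is a mislabelled sentence. This stands in part. A reader might infer that the plan fixes 50% as a formal null, so that a stratum fails below 32/50 or 33/50; the documents do not say so. A reader might equally infer that sizing on mean change is established; the near match to 47.5 is suggestive, and 25 stays unexplained. On either reading, the stated inputs do not support the stated power for a response rate.

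The gap between t-test and benchmark is also easy to overstate. The 29% case is the edge of significance, not a forecast. The pilot (Protocol 5.2) reported a median rise of 1.1 g/dL in the 15 patients who completed at least 9 treatments, so at least half of those passed 1.0. What stands is that the t-test does not answer the 50% question.

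Two further inferences go too far. One is that 8.3 replaces treatment failures. Replacement is stated for withdrawn subjects, and the failures come in a separate paragraph that can be read as keeping them as non-responders. The wording is ambiguous because they are also dropped out. The 20% share also comes from a non-iron-deficient group on another iron product. The other is that the time point of response is open between week 12 and a best value. Follow-up is twelve weeks, Protocol 7.1 expects the change by then, and a best value is nowhere mentioned. Each needs only a line of clarification.

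**Conclusion.** The point holds. As written, the 90% power claim and the 25 and 47.5 figures are wrong for a response rate of 0.54 against 0.50: the requirement is about 1,335 or 1,638 per stratum, and 50 gives about 10% or 6% power (one-sided or two-sided). These figures use only the plan's inputs and take superiority over 50% as the natural reading of the sentence. Which endpoint was actually sized cannot be settled from the documents.

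It also holds, from the text alone, that two of the three primary endpoints have no test or CI and that no deciding endpoint is named. That the paired t-test can be significant with a response rate under 50% rests on the assumptions in step 6; it shows that the two questions differ and does not predict the result. The denominator and time point are minor clarifications and do not carry the conclusion.

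**What to change.** 1. In 13.1 and the SAP, say which endpoint was sized, and remove or restate the 90% power claim and the 25 and 47.5 figures. Enrolment need not rise.
2. In 13.2 and the SAP, report the response rate and the Hb above 11.0 g/dL rate in each stratum with exact 95% CIs. Interpret the response rate and its CI beside the 50% benchmark, and state that a significant paired t-test alone does not show that the benchmark is met. A pass/fail count such as 32/50 (one-sided) or 33/50 (two-sided) is optional.
3. Name the primary endpoint that decides the conclusion in each stratum, and confirm week 12 as the time point for response. The SAP is dated September 2019 and recruitment was tentatively set for 2016. If data had already been seen, label the choice as made after data collection.
4. In 8.3, clarify that patients classed as treatment failures count as non-responders in the denominator and are not among the replaced withdrawals.

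These are text changes; they need no extra patients or measurements. The sponsor gives up the 90% power statement, and the low power is not cured: with 50 per stratum the result will probably be inconclusive against 50% if the true rate is near 54%. If failures would otherwise have been replaced, item 4 also lowers the reported rate.

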#### 5.2 Aim of Study

In a previous pilot study conducted by our group, we investigated the use of IV iron without ESAs in a group of non-iron deficient anemic cancer patients undergoing chemotherapy. Patients were given 12 weekly short infusions of ferric sucrose while on chemotherapy. The mean increment in hemoglobin level for the 15 patients who completed at least 9 treatments was 1.7 g/dL (median, 1.1 g/dL; range, -1.9 g/dL to 3.2 g/dL). Five (20.0%) patients were transfused and considered as treatment failures. No treatment-related adverse events were reported.

With such results and to move forward with the investigation, we have considered using a new intravenous iron formulation. Ferric carboxymaltose (FCM), is widely used to treat iron deficiency anemia in different clinical settings including pregnancy-related and in chronic renal failure patients..

Therefore, the study aims to investigate the effect of FCM without ESAs on anemic cancer patients undergoing chemotherapy or radiotherapy; stratified by status of iron deficiency (i.e. non-iron deficient vs. iron deficient patients).

Furthermore, we aim to investigate the value of Hepcidin and also CRP (which is closely associated with inflammatory cytokines, as well) as predictors of response.

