#### 10.3 Follow-up

- Hemoglobin assessments will be carried out every 3 weeks in line with the chemotherapy protocol visits and at week 12.
- Laboratory monitoring of ALT, AST, LDH, Alk-phosphatase, GGT and phosphorous will be done at week-3
- Ferritin level will be repeated at week-12
- A total of four follow-up visits are required for the study: weeks 3, 6, 9 and 12.

Figure 1 Study Scheme

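### Read as written, the week-12 mean Hb change is most naturally a completer mean, and it overstates the gain if patients dropped as treatment failures did worse

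*SAP*

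**What the plan says.** Protocol section 6.3.1 lists three primary endpoints. The third is "The mean Hb change from baseline to week 12".

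The analysis section is the same in the SAP and in protocol section 13.2. Its only test for Hb means is this one: "Comparison between means of Hb level will be made between the baseline Hb and Hb levels in the following weeks using Paired T-test". Mean, median, range and average percent change are descriptive.

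Protocol section 8.3 states what happens to some patients during follow-up: "Additionally, patient will be dropped out and will be considered treatment failure if" one of two events occurs. The first is "Receive ESA or blood transfusion for medical reasons not related to the study". The second is a grade IV toxicity, possibly due to the study drug, arising between the two doses. The same section adds: "Withdrawn subjects will be replaced to have a complete set of 50 analyzable subjects in each strata". It does not say whether a patient dropped as a failure counts as withdrawn for this purpose.

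Hb is measured at baseline and at the visits in section 10.3: "A total of four follow-up visits are required for the study: weeks 3, 6, 9 and 12". Neither document defines an analysis set for mean change, a rule for missing Hb, a rule for Hb measured after a transfusion or ESA, or a sensitivity analysis.

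**The concern.** A paired t-test at week 12 needs an Hb at baseline and at week 12. A patient dropped before week 12 has no second value unless a rule supplies one, and none does. Being called a treatment failure settles a responder endpoint, because a failure can be scored as a non-responder. It does not say what Hb change to enter in a mean. With a target of 50 analysable patients per stratum and replacement of withdrawals, the plan points to a mean over those who stayed.

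Dropping is unlikely to be unrelated to the outcome. Transfusion and ESAs treat anemia, and Hb is what the endpoint measures. There is no control arm, so the mean change in each stratum will be read as the effect of FCM, and nothing in the design would expose an upward shift.

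**Working it through.** The plan gives no figure for this bias, so there is none to reproduce. The size has to be worked out under stated assumptions.

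**Inputs**
- Share dropped, q: 10% (the drop-out allowance in the sample size section, which covers all causes) and 20% (the share transfused in the pilot, protocol section 5.2). Both are illustrative; neither is an estimate of the failure share in this trial.
- SD: 1.21, from the sample size section. It is printed without a unit and beside a proportion. Reading it as the SD of Hb change in g/dL over all treated patients is an assumption.
- Difference in mean change, d = stayers minus dropped: not in the documents. Assumed range 0 to 2 g/dL.
- Patients analysed per stratum, n: 50 if dropped patients are replaced; 45 or 40 if 10% or 20% of 50 are dropped and not replaced.

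**Step 1. Size of the overstatement.** The all-patient mean is (1 − q) × (stayer mean) + q × (dropped mean). Subtracting it from the stayer mean leaves q × d.

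| q | d = 0 | d = 1 | d = 2 |
|---|---|---|---|
| 10% | 0 | 0.1 | 0.2 |
| 20% | 0 | 0.2 | 0.4 |

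**Step 2. Ceiling.** If changes are normal and exactly the lowest share q is dropped, the overstatement is 1.21 × φ(z_q) / (1 − q), where φ is the standard normal density at the q quantile.
- q = 10%: 1.21 × 0.1755 / 0.9 = 0.236 g/dL (d = 0.236 / 0.1 = 2.36).
- q = 20%: 1.21 × 0.2800 / 0.8 = 0.423 g/dL (d = 0.423 / 0.2 = 2.12).

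**Step 3. Moderate link.** If the tendency to be dropped has correlation ρ with low Hb change (bivariate normal), the overstatement is ρ × ceiling. For ρ = 0.3 to 0.5:
- q = 10%: 0.071 to 0.118 g/dL.
- q = 20%: 0.127 to 0.212 g/dL.

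**Step 4. Effect on the test.** Suppose the true all-patient mean change is zero. The two-sided 5% paired t-test then has noncentrality bias × √n / 1.21.

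| Bias (g/dL) | n = 40 | n = 50 |
|---|---|---|
| 0 | 5.0% | 5.0% |
| 0.1 | 8.0% | 8.8% |
| 0.2 | 17.5% | 20.9% |

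For a bias of 0.2 the noncentralities are 0.2 × 6.325 / 1.21 = 1.045 (n = 40) and 0.2 × 7.071 / 1.21 = 1.169 (n = 50).

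If the true mean change were 0.9 g/dL (an illustrative value), power is 0.996 at n = 40 and 0.999 at n = 50. The test then rejects with or without the bias, and only the estimate moves.

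**The case against.** **No sentence excludes failures from the Hb comparison.** This stands: exclusion is inferred from section 8.3, the need for paired values and the absence of any missing-data rule. Failures can contribute pairs at visits before they drop, so the loss is at week 12. Hb follows the chemotherapy visits, so later values may exist. But if Hb after a transfusion or ESA were kept, part of the rise would be due to rescue and the gain could again be inflated. A rule is needed either way.

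**The direction is not established.** This stands too. The wording of the ESA and transfusion trigger is unclear about why patients are rescued, no Hb change is given for dropped patients, and the direction for toxicity failures is unknown. Step 1 therefore starts at zero.

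**Other outputs cover failures.** The response rate can count them as non-responders, and transfusion and ESA counts will be reported. That makes rescue visible, but it does not correct the mean, which is a separately listed primary endpoint.

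**The bias is small beside the sampling error.** With SD 1.21, the 95% CI half-width is about 0.34 g/dL at n = 50 and 0.39 at n = 40, larger than the moderate-link values. That tempers the point. Still, the interval does not show the bias, and replacement does not reduce it.

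**A mixed model also lacks week-12 values for rescued patients.** True, but it uses their earlier Hb, which the week-12 paired test discards. It does little for toxicity failures, who drop before the first follow-up Hb at week 3.

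Three stronger readings are tempting and not supported:
- *That the pilot demonstrates the bias.* Section 5.2 says "Five (20.0%) patients were transfused and considered as treatment failures" and also "The mean increment in hemoglobin level for the 15 patients who completed at least 9 treatments was 1.7 g/dL". Five being 20.0% implies 5 / 0.200 = 25 patients, so the mean covers 15 / 25 = 60% of them. The protocol does not say whether the five transfused patients were outside the 15. The pilot also used another iron product, weekly infusions and only non-iron-deficient patients.
- *That the overstatement could reach 0.72 g/dL*, by giving 20% of patients the pilot's lowest change: 0.2 × (1.7 + 1.9) = 0.72. This makes every failure as bad as the single worst pilot patient, and it exceeds the 0.42 ceiling in step 2.
- *That the test has a 21% error rate.* That figure needs a true change of zero, a bias of 0.2 g/dL and 50 patients analysed after replacement.

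**Conclusion.** The point holds as a conditional one. A listed primary endpoint has a single named test and no rule for patients whom the protocol itself removes, so on its natural reading the week-12 result is a completer mean. If dropped patients have lower Hb changes, the gain is overstated by the share dropped times the difference in mean change. Under an SD of 1.21 g/dL, roughly normal changes and a moderate link, that is about 0.07 to 0.12 g/dL at 10% dropped and 0.13 to 0.21 at 20%, with ceilings of about 0.24 and 0.42. If dropped patients do no worse, it is zero.

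The consequence is mainly for the estimate, which in a single-arm study is the result. The test's conclusion could change only if the true change is near zero. The documents do not support saying that failures are expressly excluded, that bias is certain, or that the response rate shares the problem.

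**What to change.** In the SAP, and in protocol section 13.2 to match:

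1. Define the analysis set for mean change as all treated patients in each stratum. State that enrolling a replacement never removes a treatment failure from it.
2. Estimate the week-12 absolute change (g/dL, 95% CI) with one repeated-measures mixed model per stratum. Use the Hb already scheduled at baseline and the four follow-up visits, with baseline as one of the repeated outcomes so that every treated patient enters. Leave out Hb measured after a transfusion or ESA.
3. State that this estimates the mean change without rescue, assuming the missing values are missing at random, and that patients with only a baseline Hb add little to it.
4. Add a sensitivity analysis that gives failures their last pre-rescue change (zero if none) and then, as a stress test, a range of values below zero. This is also what covers failures with no Hb after baseline.

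The change needs no new data or visits, and SAS is already planned. It costs a little more analysis work and a missing-at-random assumption to defend, and the estimate may be less favourable. None of it alters when patients are treated, rescued or dropped.
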